Seroprevalence of *Bordetella pertussis* antibodies and anti-pertussis antibody response after a single dose of Tdap in pregnant Thai women

NCT number: NCT 03498300

Document date: March 11, 2020

Background: Maternal immunization with tetanus toxoid, reduced diphtheria toxoid, and acellular pertussis vaccine (Tdap) has recently been implemented to prevent infant pertussis. Tdap is still not routinely recommended in Thailand, and there are limited data to support or challenge this strategy.

Objectives: The primary aim was to determine the seroprevalence of anti-pertussis toxin antibodies (anti-PT IgG) among pregnant Thai women. The secondary aims were to evaluate antibodies response after Tdap vaccination between seronegative and seropositive mothers and to compare the different antibody titers at delivery among seropositive mothers who received Tdap to those who received tetanus-diphtheria vaccine (Td).

Methods: This randomized clinical trial was conducted during April 2018 to April 2019 at Siriraj Hospital, Bangkok, Thailand. A total of 129 pregnant women were included. Paired blood samples for anti-PT IgG levels were obtained during the first antenatal visit and at delivery. A baseline cut-off value of <5 IU/ml indicated seronegativity. All seronegative participants (n=69) received Tdap, while the seropositive group were randomized 1:1 to receive either Tdap (n=18) or Td (n=13) during 27-36 weeks' gestation. The antibody levels from both sera were compared between groups.

Statistical analysis: All data analyses were performed using PASW Statistics version 18.0 for Windows (SPSS, Inc., Chicago, IL, USA). Descriptive data are presented as number and percentage, mean \pm standard deviation, or median and range (minimum–maximum), as appropriate. One-way analysis of variance (ANOVA) and Kruskal-Wallis test was used to compare continuous variables with and without normal distribution among 3 groups, respectively. Either Pearson's chi-square test or Fisher's exact test was used to compare qualitative characteristics among groups. Comparison of anti-PT IgG levels between the first antenatal care (ANC) and during delivery in each group was performed using Wilcoxon test. Mann-Whitney U test was used to evaluate antibody response after Tdap vaccination between seronegative and seropositive mothers (group 1 vs. group 2), and to compare the different anti-PT IgG levels of paired serum samples among seropositive mothers between those who received Tdap and those who received Td (group 2 vs. group 3). Spearman's rho analyses were performed to examine the correlation of the increment of anti-PT IgG titers with the interval of Tdap vaccination and delivery. A p-value <0.05 was considered statistically significant.

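### The group 1 vs group 2 comparison is non-randomised but unadjusted, and the only described check on group differences is a three-group significance test with limited power

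*Combined protocol and SAP*

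**What the plan says.** The document's Methods paragraph forms group 1 by a laboratory rule: "A baseline cut-off value of <5 IU/ml indicated seronegativity", and "All seronegative participants (n=69) received Tdap". Only the seropositive women were "randomized 1:1 to receive either Tdap (n=18) or Td (n=13"). Groups 2 and 3 are therefore randomised arms, and group 1 is not.

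The Objectives paragraph lists the antibody response of seronegative against seropositive mothers as a secondary aim. The Statistical analysis section gives the method: "Mann-Whitney U test was used to evaluate antibody response after Tdap vaccination between seronegative and seropositive mothers (group 1 vs. group 2"). It describes no covariate adjustment.

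Characteristics are compared across groups in two ways. For continuous variables, "One-way analysis of variance (ANOVA) and Kruskal-Wallis test was used to compare continuous variables with and without normal distribution among 3 groups". For the rest, "Either Pearson's chi-square test or Fisher's exact test was used to compare qualitative characteristics among groups". The threshold is the usual one: "A p-value <0.05 was considered statistically significant". The variables are not named, and no outcome analysis is said to use the results. The section also correlates the rise in titre with the Tdap-to-delivery interval by Spearman's rho, as a separate analysis.

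**The concern.** Women below and above the 5 IU/ml cut-off may differ in more than serostatus. Any such factor that also affects the delivery titre will be mixed into the group 1 vs 2 difference, and a rank test with no covariates cannot separate the two. The described check does not help much. It gives one p-value for three groups, it does not show how large the group 1 vs 2 difference is, and it feeds into nothing. What is at stake is the interpretation of one secondary aim: a difference in response could be credited to prior immunity when part of it comes from, for example, a different interval between vaccination and delivery.

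**Working it through.** The documents give no sample-size calculation, SDs or baseline data, so there is no stated figure to reproduce. The imbalance sizes below are assumptions, shown as a range.

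**Inputs.** Group sizes 69, 18 and 13 (Methods), total 100; significance level 0.05 (Statistical analysis). Equal SDs and two-sided pairwise tests are assumed. A factor linked to serostatus is taken to shift groups 2 and 3 equally, because both were randomised from the same seropositive women.

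**1. Power of the three-group ANOVA.** The noncentrality is λ = Σ n_j(μ_j − μ̄)²/σ². With groups 2 and 3 both shifted by d SD, λ = (69 × 31/100)d² = 21.39d². The critical value of F on 2 and 97 df is 3.09.

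| d (SD) | λ | Power | Missed |
|---|---|---|---|
| 0.3 | 1.93 | 21% | 79% |
| 0.5 | 5.35 | 52% | 48% |
| 0.7 | 10.48 | 82% | 18% |
| 0.8 | 13.69 | 91% | 9% |

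Power reaches 50% at 0.49 SD and 80% at 0.68 SD. Simulated Kruskal-Wallis power (4,000 runs) is close: 20%, 49% and 90% at 0.3, 0.5 and 0.8 SD. For a binary factor, the three-group chi-square test has power of about 36% for 50% vs 30%, and 74% for 50% vs 20% (20,000 runs).

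**2. Does pooling three groups cause the low power?** A separate t-test of 69 vs 18 has standard error √(1/69 + 1/18) = 0.265 SD. At 0.5 SD the noncentrality is 0.5/0.265 = 1.89 and the power is 46%, below the 52% of the three-group test. Pooling loses power only if group 2 alone differs. Then λ = (18 × 82/100)d² = 14.76d², which is 3.69 at 0.5 SD, for 38% power against 46%. That pattern would be a chance imbalance between the randomised arms, not a factor tied to serostatus.

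**3. What a non-significant result leaves open.** The 95% CI half-width for a group 1 vs 2 difference is 1.988 × 0.265 = 0.53 SD. Splitting the test would not cure the problem.

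**4. Effect on the outcome test.** Assume no true serostatus effect, one covariate shifted 0.5 SD between groups 1 and 2, and a within-group correlation ρ between covariate and log titre. The outcome then shifts by 0.5ρ, which is 0.15, 0.25 and 0.35 SD for ρ = 0.3, 0.5 and 0.7. With 20,000 simulated trials of 69 vs 18, the unadjusted Mann-Whitney test rejects about 8%, 15% and 24% of the time (t-test by formula: 9%, 15% and 26%). A regression that includes the covariate rejects about 5% in each case.

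**The case against.** The strongest objection is that the aim is descriptive. Serostatus is not an assigned treatment, the document makes no causal claim about it, and an unadjusted comparison does answer how the two kinds of mother differ. No confounder is shown to exist, and its direction is unknown. This stands in part. It is why the Mann-Whitney result should stay and the adjusted analysis should sit beside it. It does not remove the need to tell readers how much of the difference survives adjustment.

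Four stronger readings are tempting, and the documents do not support them:

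- A reader might infer that comparability is formally judged by this test and that p≥0.05 licenses the unadjusted analysis. The section says only that variables were compared.
- A reader might call group 1 self-selected. It is set by a laboratory cut-off, and no choice by the women is described.
- A reader might conclude that a confounder will usually go undetected. For a shared shift this holds only below about 0.49 SD; at 0.7 SD the ANOVA finds it 82% of the time. The 38% figure at 0.5 SD belongs to the group-2-only pattern.
- A reader might blame the mixing of randomised and non-randomised groups. For a serostatus-linked factor, pooling slightly raises power.

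Nor can every group 2 vs 3 difference safely be called chance. The three groups sum to 100 of the 129 women included, and the text does not account for the other 29. Some may have been lost after randomisation.

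**Conclusion.** The point holds in a limited form. The group 1 vs 2 contrast is non-randomised and unadjusted, and a non-significant three-group test with these numbers cannot exclude an imbalance of 0.3 to 0.5 SD (power 21% to 52%). If a 0.5 SD imbalance existed on a covariate correlated 0.3 to 0.7 with the outcome, the unadjusted test would reject falsely about 8% to 25% of the time instead of 5%. These figures rest on assumed shifts and correlations, normal data with equal SDs, and the stated group sizes; including any of the 29 unaccounted women would change them. They show what could go undetected, not that any imbalance occurred. The primary aim (seroprevalence) and the randomised group 2 vs 3 comparison are not affected.

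**What to change.** Keep the Mann-Whitney test and add beside it a linear regression of log delivery titre on serostatus group in groups 1 and 2 (69 + 18 = 87 women). Adjust for a short list of covariates already collected, chosen on clinical grounds and regardless of any p-value, including the Tdap-to-delivery interval that the plan already analyses. The document names no other characteristics, so the list has to be written down. Baseline anti-PT titre should not be on it: the cut-off defines the groups, so they do not overlap on that variable. Report the adjusted ratio of delivery titres with a 95% CI.

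Label this a sensitivity analysis, because the document is dated March 2020 and the trial ran from April 2018 to April 2019. Describe the group 1 vs 2 contrast as observational wherever it is reported. Standardised differences for 1 vs 2 and 2 vs 3, shown separately, are an optional reporting change that alters no result.

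The cost is one regression on existing data and a few degrees of freedom out of 87.

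### The first-visit titre that sorts the groups appears also to be the starting value for change, so changes within groups 1 to 3 and between groups 1 and 2 can include regression to the mean; the randomised comparison escapes this but states no baseline adjustment.

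*Combined protocol and SAP*

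**What the plan says.** Under Methods, two samples per woman are described: "Paired blood samples for anti-PT IgG levels were obtained during the first antenatal visit and at delivery". Groups are formed from the titre: "A baseline cut-off value of <5 IU/ml indicated seronegativity". For group 1, "All seronegative participants (n=69) received Tdap". Only seropositive women were randomised, 18 to Tdap (group 2) and 13 to Td (group 3).

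The Statistical analysis section plans three uses of the titres that bear on this point:
- within each group: "Comparison of anti-PT IgG levels between the first antenatal care (ANC) and during delivery in each group was performed using Wilcoxon test";
- between the two Tdap groups: "Mann-Whitney U test was used to evaluate antibody response after Tdap vaccination between seronegative and seropositive mothers (group 1 vs. group 2");
- between the randomised arms, a Mann-Whitney test "to compare the different anti-PT IgG levels of paired serum samples among seropositive mothers".

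For the randomised arms, Objectives puts the aim differently: "to compare the different antibody titers at delivery among seropositive mothers who received Tdap". A change measure is named only for the Spearman analysis, which concerns "the increment of anti-PT IgG titers with the interval of Tdap vaccination and delivery". Antibody response is not defined, and no covariate adjustment is described for any comparison.

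**The concern.** No separate screening sample or repeat pre-vaccination sample is described. The titre that assigns a woman to a group therefore appears to be the one from which her change is measured. Sorting on a noisy value selects women whose first reading was low by chance into group 1, and women whose first reading was high by chance into groups 2 and 3. Their second readings then tend to drift back, with or without vaccine.

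Two things are at stake. First, a before/after difference within a group cannot separate a Tdap effect from this drift. Group 1 has no unvaccinated seronegative control to show the drift alone. The same problem reaches group 1 vs group 2, a stated secondary aim, if antibody response means any measure of change, because the drift runs in opposite directions in the two groups. Second, the one comparison free of this problem is small (18 vs 13), and the plan does not say that it uses the first-visit titre to gain precision.

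**Working it through.** The documents state no SD, correlation, effect size or power, so there is no planned figure to reproduce. What follows sizes the effect under assumptions.

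**Inputs from the documents:** cut-off 5 IU/ml; group sizes 69, 18 and 13; 129 women included. The three groups sum to 100, so the share below the cut-off is taken both ways: p = 69/129 = 0.535 and p = 69/100 = 0.69.

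**Assumptions:** titres log-normal and fully measured below 5 IU/ml; first-visit SD of ln titre, s, 0.8–1.2; correlation r between visits without vaccine effect 0.7–0.99; k = delivery SD / first-visit SD, also without vaccine effect.

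**Step 1. Shift with no true change.** The expected change in ln titre is (r × k − 1) × (group mean − overall mean) at the first visit. With c the normal quantile of p, the group mean lies −s × φ(c)/p from the overall mean in group 1 and +s × φ(c)/(1 − p) in groups 2 and 3.
- p = 0.535: c = 0.088, φ(c) = 0.397; distances −0.743s and +0.854s.
- p = 0.69: c = 0.496, φ(c) = 0.353; distances −0.511s and +1.138s.

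Examples at r = 0.9, k = 1, s = 1.2: group 1 with p = 0.535 gives exp(0.1 × 0.743 × 1.2) = 1.09; groups 2 and 3 with p = 0.69 give exp(−0.1 × 1.138 × 1.2) = 0.87. Over all settings:

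| r | k | Group 1 | Groups 2 and 3 |
|---|---|---|---|
| 0.99 | 1 | up to x1.01 | x0.99 |
| 0.95 | 1 | x1.02–1.05 | x0.93–0.97 |
| 0.9 | 1 | x1.04–1.09 | x0.87–0.93 |
| 0.7 | 1 | x1.13–1.31 | x0.66–0.81 |
| 0.9 | 0.8 | x1.12–1.28 | x0.68–0.83 |
| 0.8 | 1.25 | x1.00 | x1.00 |
| 0.9 | 1.25 | x0.89–0.95 | x1.09–1.19 |

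The shift vanishes when r × k = 1 (0.8 × 1.25) and reverses above 1 (0.9 × 1.25 = 1.125).

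**Step 2. Group 1 vs group 2 on change** (simulation, k = 1). The figure is the share of trials in which a two-sided 5% Mann-Whitney test falsely favours group 1; nominal 2.5%.
- Raw increment, no true change: roughly 30–38% at r = 0.9 and 60–70% at r = 0.7.
- Fold change, same true doubling in every woman: 6% at r = 0.99, 15–16% at 0.95, 26–27% at 0.9, 65–69% at 0.7. If individual responses vary with SD(ln) 0.5, this is 12–16% at 0.9; with SD(ln) 1.0, 6–9%.
- On the raw increment, an equal true fold rise also produces a larger increment in group 2, simply because its titres start higher. With a uniform doubling at r = 0.9 the test favours group 2 in 83–96% of trials. That is a scale effect, opposite in direction to the drift.

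**Step 3. Group 2 vs group 3.** Both arms come from the same seropositive pool, so the drift is common to both and cancels; simulated rejection with no effect is 4–5%, on delivery titre or on change. The gain from adjustment is in precision. The difference detectable with 80% power is (1.96 + 0.84) × √(1/18 + 1/13) = 1.02 SD unadjusted. Adjustment multiplies it by √(1 − q²), where q is the correlation among seropositive women: 0.88 SD at q = 0.5 and 0.73 SD at q = 0.7. Truncation at the cut-off makes q lower than r (q = 0.45–0.87 for r = 0.7–0.95).

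Power for a true doubling, adjusted model against Mann-Whitney on delivery titre alone (simulation, k = 1):

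| Response SD(ln) | r = 0.9 | r = 0.7 |
|---|---|---|
| 0.5 | 80–95% vs 54–83% | 49–76% vs 41–70% |
| 1.0 | 50–59% vs 39–54% | 34–48% vs 31–47% |

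Against a Mann-Whitney test on fold change, the adjusted model differs by only −4 to +3 points.

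**The case against.** The plan lists the per-group Wilcoxon tests but never says that they demonstrate a Tdap effect. Both secondary aims are comparisons between groups, and the randomised comparison is already one of them with a named test. That stands: a reader might infer that the plan rests its case for Tdap on the before/after tests, but the documents do not say so.

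A rank test for skewed titres in arms of 18 and 13 is defensible, and the reference to paired samples may mean that the first-visit titre already enters the randomised comparison as a change. That also stands. On that reading the adjusted model offers little or nothing, and on no reading is the unadjusted randomised test invalid.

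Size and direction are undetermined. With a correlation near 1 and equal SDs the shift is trivial, and a real vaccine response could dwarf it. A reader might infer that an observed rise in group 1 would be an artefact; nothing in the documents supports that.

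Finally, the document is dated March 2020, after a study period that ended in April 2019, and it reports its analyses in the past tense. A model added now would be post hoc and should be labelled so.

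What survives is narrower: the per-group tests, and group 1 vs group 2 on any change measure, cannot be read as isolating a Tdap effect or a true difference in response, and the text does not warn of this.

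**Conclusion.** The point holds as a cheap improvement in analysis and reporting, not as an error in the plan. Changes in all three groups, and a group 1 vs group 2 contrast based on raw increment or fold change, can include regression to the mean. This rests on the inference that the classifying titre is also the starting value. The shift raises group 1 and lowers groups 2 and 3 only if correlation × SD ratio is below 1, which the documents do not let one check. A plausible size runs from negligible to about 30% in either direction.

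It would go too far to call the randomised comparison biased. Missing adjustment there is a loss of precision: material if the test uses delivery titre alone and responses are fairly uniform, small or nil if it uses change or responses vary widely. Its freedom from bias also assumes no selective loss after randomisation, which the documents do not address. Seroprevalence does not depend on any of this.

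**What to change.** 1. For group 2 vs group 3, report log delivery titre adjusted for log first-visit titre as a geometric mean ratio with 95% CI, alongside the Mann-Whitney test and labelled post hoc if the data have already been analysed. State whether the Mann-Whitney test is on delivery titre or on change.
2. Define antibody response for group 1 vs group 2: delivery titre, raw increment or fold change. If it is a change measure, say that the difference can include regression to the mean in opposite directions; if it is the raw increment, mention the scale effect too.
3. Present the per-group Wilcoxon results as descriptive, and name regression to the mean and the lack of an unvaccinated seronegative control as limitations. In group 2 the drift cancels against group 3; for group 1 the design offers no such correction.

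No new data are needed. The cost is one model-based analysis in arms of 18 and 13, whose log-scale assumptions should be checked, and a few sentences of text.

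### The non-randomised group 1 vs group 2 comparison of response to Tdap makes no allowance for the dose-to-delivery interval, so a systematic difference in sampling time could be read as a serostatus effect or could hide one

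*Combined protocol and SAP*

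**What the plan says.** - **Groups (Methods).** "A baseline cut-off value of <5 IU/ml indicated seronegativity". Group 1 is every woman below that cut-off: "All seronegative participants (n=69) received Tdap". Group 2 is the Tdap arm of the seropositive women: "the seropositive group were randomized 1:1 to receive either Tdap (n=18) or Td (n=13) during 27-36 weeks' gestation". Group 2 was therefore randomised against group 3 only. The gestational window is worded for the randomised women. Applying it to group 1 as well is the natural reading, and no other window is given.
- **Sampling (Methods).** "Paired blood samples for anti-PT IgG levels were obtained during the first antenatal visit and at delivery". Titre is measured twice, but only the delivery sample follows the dose.
- **Test for groups 1 and 2 (Statistical analysis).** "Mann-Whitney U test was used to evaluate antibody response after Tdap vaccination between seronegative and seropositive mothers (group 1 vs. group 2"). No covariate, stratification or matching is stated.
- **Use of the interval (Statistical analysis).** A Spearman analysis examines the "correlation of the increment of anti-PT IgG titers with the interval of Tdap vaccination and delivery". It is a separate analysis, and the text does not say whether it is pooled or done within groups.

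**The concern.** The post-dose sample is tied to delivery, not to a fixed time after the dose. Two women with the same antibody curve can give different readings because one was vaccinated early in the window and the other late. By planning the Spearman analysis, the authors treat the interval as a possible determinant of the rise in titre. The contrast that answers the first secondary aim nevertheless leaves it out, and randomisation does not balance it between groups 1 and 2.

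At stake is the interpretation of that contrast. If one group was typically sampled later after its dose, the test compares different points on the post-vaccination curve. A difference could then be credited to serostatus when it reflects timing, or a real difference could be masked. The Spearman result cannot settle this: it asks whether rise and interval are related, and it does not remove an interval difference from the group comparison.

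**Working it through.** The documents give no sample-size calculation, SD, interval distribution or decline rate, so there is no figure to reproduce. The check asks how large the effect could be if the conditions for it held.

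**From the documents:** n = 69 (group 1) and 18 (group 2); dosing at 27-36 weeks; one post-dose sample, at delivery; significance at p < 0.05, taken as two-sided.

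**Assumed:** delivery at 37-41 weeks; interval SD 2.5 weeks; log-linear decline after the peak with half-life 6 or 10 weeks; residual SD of log titre 0.8; no true serostatus effect.

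**1. Possible spread of the interval.** Longest: 41 − 27 = 14 weeks. Shortest: a dose at 36 weeks 6 days and delivery at 37 weeks gives 37 − 36 − 6/7 ≈ 0.1 week.

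**2. False titre ratio from a gap *d* in mean interval.** Ratio = 2^(d/half-life).
- 1 week: 2^(1/10) = 1.07 to 2^(1/6) = 1.12
- 2 weeks: 2^(2/10) = 1.15 to 2^(2/6) = 1.26
- 3 weeks: 2^(3/10) = 1.23 to 2^(3/6) = 1.41

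**3. False-positive rate, by simulation (2,000 runs per setting, 69 vs 18).**

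| Systematic gap | Mann-Whitney, half-life 10 weeks | Mann-Whitney, half-life 6 weeks |
|---|---|---|
| 1 week | 5.4% | 8.2% |
| 2 weeks | 9.9% | 16.1% |
| 3 weeks | 14.1% | 29.3% |

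A model with group plus a linear interval term rejected in 4.6-5.1% of runs. Repeating the simulation moves the unadjusted figures by about a percentage point, hence the rounded ranges 5-8%, 9-16% and 14-30%.

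**4. Second parameterisation (4,000 runs per setting).** Here the strength of the relation is set by the within-group correlation between log response and interval.
- Correlation 0: about 5% at every gap.
- No gap: about 5% at every correlation.
- Correlation 0.3: 7.2%, 14.1% and 25.2% for gaps of 1, 2 and 3 weeks.
- Correlation 0.5: 10.9%, 30.3% and 59.7%.
- Interval-adjusted model: 4.0-5.2% throughout.

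The two sets agree. With half-life 6 weeks, the interval contributes an SD of (ln 2 / 6) × 2.5 = 0.289 on the log scale, so the implied correlation is 0.289/√(0.8² + 0.289²) = 0.34. With half-life 10 weeks it is 0.173/√(0.8² + 0.173²) = 0.21. A correlation of 0.5 is therefore a steeper decline than step 3 assumes.

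**5. What chance alone can do.** The standard error of the difference in mean interval is 2.5 × √(1/69 + 1/18) = 0.66 weeks. If both groups come from one interval distribution, the probability of a gap of at least 1 week is about 13% (z = 1/0.66 = 1.51). For at least 2 weeks it is about 0.25% (z = 3.02), and for at least 3 weeks about 0.0006%. Simulating both groups from one distribution (10,000 runs per half-life), Mann-Whitney rejected in 4.6% of runs for each half-life.

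**The case against.** Much of the case on the other side stands.

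- **Chance imbalance.** A reader might infer that, with only 18 women in group 2, an interval gap is likely by chance and inflates the error rate. It does not. Gaps of 2-3 weeks almost never arise by chance under the assumed SD, and the nominal 5% already covers chance gaps. Inflation needs a systematic gap.
- **Whether a gap exists.** A reader might also infer that the groups did differ in interval. Nothing in the documents shows this. They describe one hospital and one stated window, and nothing links serostatus to vaccination week or delivery date. What remains is that the design does not rule such a link out, because the contrast is observational.
- **The plan does not ignore the interval.** It must be recorded for the Spearman analysis, and the three-group ANOVA or Kruskal-Wallis test could be applied to it, although the text does not say so. Showing an imbalance would still not adjust for it.
- **A linear interval term is not a guaranteed repair.** It returns the rate to 5% above because the data were generated with that shape. Short intervals may fall where titre is still rising. With an assumed rise to week 3 followed by decline, and a mean interval of 3 weeks in the smaller group, the linear model rejected in 10-20% of runs at gaps of 2-3 weeks. This was better than no adjustment but not 5%. With a mean of 6 weeks it stayed at about 4-6%.
- **Choice of outcome.** A model of delivery titre without baseline would mix starting level into response, because group 2 starts at or above 5 IU/ml and group 1 below it by definition.
- **Replacing the test.** The case for making the model the main analysis is debatable. The case for reporting it alongside is not.

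**Conclusion.** The concern holds in conditional form. The group 1 vs group 2 comparison is non-randomised and unadjusted, and its single post-dose reading comes at a variable time after the dose. Bias requires both a systematic interval difference between the groups and a dependence of titre on interval. The documents establish neither, so no direction or actual size can be stated.

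The false-positive rates in the working describe what would follow under the stated assumptions and are not estimates for this trial. At a 1-week gap the rate is close to nominal. The effect becomes material only at systematic gaps of 2-3 weeks, or with a steeper decline than a 6-week half-life. The point bears on a secondary aim only; the primary seroprevalence aim is unaffected.

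**What to change.** 1. Tabulate the Tdap-to-delivery interval for groups 1 and 2 (median and range, as the plan already does for other variables).
2. Keep the Mann-Whitney test. Report next to it a log-scale linear model of the same response measure (for example log fold-rise from first visit to delivery) on group plus interval. Check the interval term for curvature, for instance by adding a quadratic term.
3. State in advance that, if the two analyses disagree or the interval distributions barely overlap, the difference will not be attributed to serostatus.
4. Leave the randomised group 2 vs group 3 comparison unadjusted for interval, because delivery date falls after randomisation.

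The cost is a few lines of analysis text, one or two degrees of freedom and a slightly wider confidence interval in the added model. The interval is already needed for the Spearman analysis, so no new women, visits or samples are required. Adjusting for interval does not remove other differences that may exist between seronegative and seropositive women, and the report should say so.

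### The only randomised comparison (Tdap vs Td in seropositive women) is defined by vaccine received, not by allocation, and 29 of 129 women are unaccounted for

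*Combined protocol and SAP*

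**What the plan says.** The Combined protocol and SAP describes the randomised part in its Methods: "the seropositive group were randomized 1:1 to receive either Tdap (n=18) or Td (n=13) during 27-36 weeks' gestation". The same section gives the other counts: "A total of 129 pregnant women were included" and "All seronegative participants (n=69) received Tdap".

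The comparison of the randomised groups is stated twice, each time by vaccine received. The secondary aim under Objectives is "to compare the different antibody titers at delivery among seropositive mothers who received Tdap to those who received tetanus-diphtheria vaccine (Td". The Statistical analysis section applies the Mann-Whitney U test to paired-serum levels "among seropositive mothers between those who received Tdap and those who received Td (group 2 vs. group 3".

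The outcome needs a second blood sample: "Paired blood samples for anti-PT IgG levels were obtained during the first antenatal visit and at delivery".

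The document does not define an as-randomised population. It gives no rule for women who were randomised but not vaccinated, vaccinated off allocation or not sampled at delivery, and no missing-data method.

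**The concern.** Group 1 vs group 2 contrasts women by baseline serostatus, so it is observational. Group 2 vs group 3 is the only comparison that randomisation protects. That protection belongs to the groups as allocated. If membership depends on what happened after allocation, a difference at delivery may partly reflect which women came back for vaccination.

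Two separate problems need to be kept apart:

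- **The grouping rule.** Defining groups by vaccine received moves a crossed-over woman to the other arm and excludes a randomised woman who had no vaccine. Analysis by allocation cures this.
- **The unexplained count.** The three group sizes fall short of the number included. If some of the shortfall is randomised women without a delivery serum, they are lost under either grouping rule. Analysis by allocation does not cure this.

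**Working it through.** **Inputs (all from Methods).** 129 included; 69 seronegative, given Tdap; 18 Tdap and 13 Td among seropositive women; allocation 1:1. The document has no sample-size, power or dropout figure, so the only figure to reproduce is the participant count.

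**1. Count.** 69 + 18 + 13 = 100, which does not reproduce 129. The shortfall is 129 − 100 = 29, and 29/129 = 22.5%.

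**2. Does the 18:13 split itself show loss?** An exact two-sided binomial test of 18 out of 31 against 0.5 gives p = 0.47. The split is compatible with simple 1:1 randomisation and is no evidence of differential loss.

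**3. Range of loss from the randomised set.** Let L be the number of the 29 who were randomised seropositive women. L is not given, so it is an assumption with range 0 to 29. The number randomised is 31 + L, overall loss is L/(31 + L), and for L > 0 the arms are taken as equal.

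| L | Randomised | Overall loss | Loss, Tdap | Loss, Td |
|---|---|---|---|---|
| 0 | 31 (18:13) | 0% | 0% | 0% |
| 5 | 36 (18:18) | 5/36 = 14% | 0/18 = 0% | 5/18 = 28% |
| 15 | 46 (23:23) | 15/46 = 33% | 5/23 = 22% | 10/23 = 43% |
| 29 | 60 (30:30) | 29/60 = 48% | 12/30 = 40% | 17/30 = 57% |

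The last row needs 69 to be every seronegative woman enrolled (129 − 69 = 60 seropositive) and all 60 to have been randomised.

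**4. What such loss could do, if it occurred.** This is a simulation with no vaccine effect: standard normal log titre, two-sided Mann-Whitney at 0.05, 4,000 to 8,000 trials per scenario. The document does not state sidedness. The 18 and 13 women kept are chosen by a retention score with an assumed correlation with titre.

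| Randomised per arm | Correlation of retention with titre | Type I error | Bias in size |
|---|---|---|---|
| 30 | none | about 5% | about 0 |
| 30 | 0.3, same direction in both arms | 5% to 6% | about 0.08 SD or less |
| 30 | 0.3, Tdap arm only | 7% to 8% | 0.19 SD |
| 30 | 0.3, Td arm only | about 10% | 0.27 SD |
| 30 | 0.3, opposite directions | 21% to 22% | 0.46 SD |
| 23 | 0.3, opposite directions | about 12% | 0.31 SD |
| 18 (five Td women lost) | 0.3, Td arm only | about 6% | 0.13 SD |

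The result depends on L, on the direction of selection in each arm and on its strength. Much stronger opposite selection (retention weight exp(±titre in SD units)) gives about 14% when five Td women are lost and about 81% when all 29 are. The document gives no ground for any of these selection patterns.

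**The case against.** The strongest reply is that nothing went wrong here. The Methods sentence attaches 18 and 13 directly to the act of randomising ("the seropositive group were randomized 1:1 to receive either Tdap (n=18) or Td (n=13"), so they may well be the numbers randomised. Received may be loose wording for allocated. With a single dose crossover is unlikely, and the document reports none, nor any randomised woman left unvaccinated. Vaccination fell at 27-36 weeks and the first sample at the first antenatal visit. The timing of randomisation is not stated, so the 29 could all have left before it.

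Most of this stands. A reader might infer from 129 − 69 = 60 that 29 of 60 seropositive women were lost after randomisation. The document does not support that. The figure 69 is attached to receipt of Tdap. If all three group sizes are vaccinated or analysed counts, some of the 29 may be seronegative. If all three are enrolment counts, 18 and 13 are the randomised numbers and the 29 were not lost from the arms.

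A reader might also think that the received-vaccine rule drops women with no delivery serum. It does not: a vaccinated woman without a serum still meets the rule, and she is missing because her outcome is missing.

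The reply does not remove two facts. The received wording appears in both the aim and the test, with no allocation-based population anywhere. And the counts do not reconcile.

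**Conclusion.** The point holds in limited form. The stated rule for the only randomised contrast gives up the protection of randomisation for any crossed-over or unvaccinated woman. Separately, 29 of 129 women (22.5%) are unexplained, which leaves loss from the randomised set anywhere from 0% (0 of 31) to 48% (29 of 60). The document does not let a reader narrow that range.

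No actual bias is shown. It would be wrong to conclude that the type I error is 22%. At a correlation of 0.3, that figure requires all 29 to be randomised seropositive women and selection in opposite directions in the two arms. With all 29 lost, the error stays near 5% if loss is unrelated to titre or related in the same direction in both arms, and is about 7% to 10% if related in one arm only.

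The contrast is a secondary aim. Seroprevalence, the primary aim, is not affected by this point.

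**What to change.** 1. In Statistical analysis, change the group 2 vs group 3 sentence to compare *those randomised to Tdap and those randomised to Td*. Include every randomised woman with a delivery serum, whichever vaccine, if any, she received. Align the secondary aim with it, and keep the received-vaccine comparison as supportive.
2. Reconcile 129 with 100: give the numbers enrolled, randomised, vaccinated and sampled at delivery for each group, and say when randomisation took place.
3. If randomised women lack a delivery serum, compare first-visit titres of included and excluded women by arm. These titres should exist for every randomised woman, because they determined serostatus. Add one sensitivity analysis, for example imputation from arm and first-visit titre with a shift.

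The cost is SAP wording, one flow table and at most one sensitivity run, on data already held. The downside is slight dilution of the estimated difference if some women did not get their allocated vaccine. If no randomised woman crossed over, went unvaccinated or lacks a serum, the flow table will show it and the result is unchanged.
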